6.8.2. Rescue Therapy (Part A only)

Rescue therapy is permitted for patients experiencing protocol-defined MG clinical deterioration AND if in addition the treating physician believes that the patient's health is in jeopardy if rescue therapy is not given. An MG clinical deterioration permitting rescue therapy to be given is defined as a patient experiencing at least 1 of the following: (1) new or worsening of respiratory / bulbar symptoms or (2) at least 2-point increase of individual non-ocular MG-ADL items.

Rescue therapy will be limited to PLEX, IVIg, immunoadsorption or use of a new type of corticosteroid or an increased dose of the current corticosteroids used as stand-alone therapy or in combination. The type of rescue therapy used should be documented.

In case a patient needs rescue therapy according to the treating investigator, the Medical Director at the sponsor should be informed in addition to the Medical Monitor at the sponsor's designated CRO; whenever possible prior to actual implementation of the rescue therapy.

In situations where the treatments as listed above are given under the protocol-defined rescue criteria, patients will be discontinued early from the trial.

6.9. Medical Care of Patients After End of Study

After a patient has completed the trial, or has withdrawn/discontinued early, usual treatment will be administered, if required, in accordance with the trial site's SoC and generally accepted medical practice depending on the patient's individual needs. The sponsor will not provide any additional care to these patients.

6.10. Treatment Compliance

The investigator should promote treatment compliance by stating that compliance is necessary for the patient's safety and the validity of the trial. The prescribed dose, timing, and mode of administration may not be changed. All dates and start and end time of efgartigimod administration and any deviations from the intended regimen must be recorded.

6.11. Handling Missed Doses of Investigational Medicinal Product

Patients in need for (re-)treatment will receive 4 weekly IV infusions of efgartigimod at a dose of 10 mg/kg over a period of 1 hour during each Treatment Period, provided they are eligible.

All efforts will be done to ensure that the patient receives the 4 administrations of efgartigimod within the allowed time windows. However, if a patient misses 1 or more doses in any Treatment Period, the patient will not be discontinued from the trial or from further trial treatment and will complete all further visits and assessments according to the General Schedule of Assessments for Part A (Table 1) and for Part B (Table 2). This patient may be eligible for further Treatment Periods during the trial.

In case a dose needs to be delayed for more than 3 days, the dosing should be skipped to ensure 2 consecutive doses are given with an interval of at least 3 days.

6.12. Accountability of Investigational Medicinal Product

Detailed instructions on accountability of efgartigimod will be included in the IMP management manual (pharmacy manual).

6.13. Storage of Blood Samples in the Trial

Any remaining samples after the analysis per protocol has been completed may be stored for up to 15 years for future additional research to address any scientific questions related to efgartigimod or MG, unless this would not be allowed according to local regulations or the patient would not agree.

7. TRIAL ASSESSMENTS

7.1. Monitoring of Disease Severity

Monitoring of disease severity will be assessed using MG-ADL (Part A and B) and QMG (Part A only). The assessments, where applicable, have to be performed predose on all efgartigimod infusion days and prior to any other assessment at each visit, except for the assessment of weight (if applicable) and signing of the ICF at SEB. The MG-ADL scale needs to be performed prior to the QMG scale in Part A (Table 1).

Monitoring of disease severity for a given patient is preferentially assessed, whenever possible, by 1 and the same trained evaluator throughout the course of the trial.

7.1.1. Myasthenia Gravis Activities of Daily Living

The MG-ADL is an 8-item patient-reported scale (Appendix 1) to assess MG symptoms and their effects on daily activities. It evaluates the capacity to perform different activities of daily living such as talking, chewing, swallowing, breathing, brushing the teeth/combing the hair, or rising from a chair and it also assesses double vision and eyelid droop. It is a discrete quantitative variable in which the 8 items are rated from 0 to 3 and the total score can point from 0 to 24, with higher total scores indicating more impairment. The assessments to be performed using MG-ADL (Appendix 1) do not require any equipment to assess MG symptoms and their effects on daily activities. The scoring of MG-ADL should be performed by a trained and certified evaluator.

7.1.2. Quantitative Myasthenia Gravis

The QMG quantifies disease severity based on impairments of body functions and structures as defined by the International Classification of Functioning, Disability and Health.¹⁸

The QMG consists of 13 items (Appendix 2) that assess ocular, bulbar, and limb function. Out of the 13 items, 6 are timed tests of endurance measured in seconds. Each item has a possible score from 0-3. The total possible score is 39, where higher total scores indicate more severe impairments. It is based on quantitative testing of specific muscle groups to assess limb function. It requires minimal equipment such as spirometer, mouthpieces that fit the spirometer, nose clips, stopwatch, cups and water for swallowing tests, goniometer, dynamometer, and is based on the trained rater's examination. The scoring of QMG should be performed by a trained evaluator.

7.2. Safety

Safety assessments will consist of monitoring and recording all AEs, pregnancies, suicidality assessment (Part A only), safety laboratory testing, measurement of vital signs, ECGs, physical examinations; and other tests that are deemed critical to the safety evaluation of the trial in all patients who receive at least 1 dose of efgartigimod. As discussed in Section 7.2.1.5, any pregnancy that occurs while a patient is enrolled into the trial will also be monitored and reported according to the appropriate regulations.

The DSMB will evaluate the safety data periodically (see Section 7.2.6).

7.2.1. Adverse Events

The investigator is responsible for recording all AEs observed during the trial from the time the patient signs the ICF until the last contact of the patient.

Definition of AE: An AE is any untoward medical occurrence in a clinical trial patient whether or not a pharmaceutical product is administered, and which does not necessarily have a causal relationship with this treatment. An AE can therefore be any unfavorable and unintended sign (including an abnormal laboratory finding), symptom, or disease temporally associated with the use of a medicinal product or efgartigimod, whether or not considered related to the medicinal product or efgartigimod.

An AE can also be a new disease or exacerbation of an existing disease (a worsening in the character, frequency, or severity of a known condition), if considered clinically relevant by the investigator.

Abnormal laboratory values, or test results, physical examination findings, and other abnormal investigational findings (ie, ECG) should not be reported as AEs unless they are considered clinically significant, eg, require therapy (eg, hematologic abnormality that requires transfusion or hematological stem cell support) or lead to treatment discontinuation.

Death is not considered an AE but an outcome.

MG disease worsening, if considered clinically relevant by the investigator, can be reported as AE, provided that it is supported by a clinically relevant change in total MG-ADL score (as compared to SEB). The investigator should contact the sponsor in case of clinically relevant worsening of the disease.

Adverse Drug Reaction (ADR): Any untoward and unintended response in a patient to efgartigimod, which is related to any dose administered to that patient.

Definition of Serious AE (SAE): An SAE, experience or reaction, is any untoward medical occurrence (whether considered to be related to efgartigimod or not) that at any dose:

- Results in death
- Is life-threatening (the patient is at a risk of death at the time of the event; it does not refer to an event, which hypothetically might have caused death if it was more severe)
- Requires inpatient hospitalization or prolongation of existing hospitalization. However, a planned hospitalization related to the administration of efgartigimod is not considered an SAE

(Hospital admissions and/or surgical operations planned before a trial are not considered SAEs or if the illness or disease, which caused hospitalization, existed before the patient was enrolled in the trial, provided that it did not deteriorate in an unexpected way during the trial. However, the condition for which the surgery is required may be an AE.)

- Results in persistent or significant disability or incapacity, OR
- Is a congenital abnormality or birth defect

- Other: Medically significant events, which do not meet any of the criteria above, but may jeopardize the patient and may require medical or surgical intervention to prevent 1 of the other serious outcomes listed in the definition above. Examples of such events are blood dyscrasias (eg, neutropenia or anemia requiring blood transfusion, etc.) or convulsions that do not result in inpatient hospitalization

Suspected Unexpected Serious Adverse Reactions (SUSARs) and Unexpected Adverse Reactions: Any suspected adverse reaction that is serious, unexpected, and considered to be related to drug exposure is defined as a SUSAR.

An unexpected AE is any adverse drug event, which is not listed in the current IB or is not listed at the specificity or intensity that has been observed.

Suspected adverse reaction means any AE for which there is a reasonable possibility that the drug caused the AE.

An untoward and unintended post-dosing response to a non-trial drug is, by definition, not a SUSAR, but is, however, an AE.

Each AE is to be evaluated for duration, severity, seriousness and causal relationship to efgartigimod or trial procedures. The action taken with the investigational drug and the outcome of the event must also be recorded.

Treatment-emergent adverse event (TEAE): Any AE temporally associated with the use of efgartigimod, whether considered related to efgartigimod or not. TEAEs are recorded from the start of efgartigimod administration, until completion of the patient's last visit.

Overdose

For the purposes of this trial, exceeding the dosage requirements specified in this protocol (see Section 6.1) represents an overdose. In case of suspected overdose, the patient should be treated according to standard medical practice based on the investigator's judgment.

Severity

All AEs observed will be graded using the National Cancer Institute (NCI) Common Terminology Criteria for Adverse Events (CTCAE) version 5.0. The NCI-CTCAE is a descriptive terminology, which can be utilized for AE reporting. A grading (severity) scale is provided for each AE term. Grade refers to the severity of the AE. If a particular AE's severity is not specifically graded by the guidance document, the investigator is to use the general NCI-CTCAE definitions of Grade 1 through Grade 5 following his or her best medical judgment. The CTCAE displays Grades 1 through 5 with unique clinical descriptions of severity for each AE based on the following general guideline:

- Grade 1: Mild; asymptomatic or mild symptoms; clinical or diagnostic observations only; intervention not indicated.
- Grade 2: Moderate; minimal, local or non-invasive intervention indicated; limiting age--appropriate instrumental activities of daily living (ADL).
- Grade 3: Severe or medically significant but not immediately life-threatening; hospitalization or prolongation of hospitalization indicated; disabling; limiting self-care ADL.

- Grade 4: Life-threatening consequences; urgent intervention indicated.
- Grade 5: Death related to AE.

Relationship

The causal relationship between efgartigimod/trial procedures and the AE has to be characterized as unrelated, unlikely, related, possible, and probable.

- Events can be classified as “unrelated” if there is not a reasonable possibility that efgartigimod caused the AE.
- An “unlikely” relationship suggests that only a remote connection exists between efgartigimod and the reported AE. Other conditions, including chronic illness, progression or expression of the disease state, or reaction to concomitant medication, appear to explain the reported AE.
- A “related” relationship suggests that the AE follows a reasonable temporal sequence from administration of efgartigimod, it follows a known or expected response pattern to efgartigimod and it cannot reasonably be explained by known characteristics of patient’s clinical state.
- A “possible” relationship suggests that the association of the AE with efgartigimod is unknown; however, the AE is not reasonably supported by other conditions.
- A “probable” relationship suggests that a reasonable temporal sequence of the AE with drug administration exists and, in the investigator’s clinical judgment, it is likely that a causal relationship exists between the drug administration and the AE, and other conditions (concurrent illness, progression or expression of disease state, or concomitant medication reactions) do not appear to explain the AE.

In final evaluation for reporting, the relationship will be converted into “Binary Determination” as per Council for International Organizations of Medical Sciences (CIOMS). Unrelated and Unlikely will be clubbed into “Unrelated” and Related, Possible and Probable will be clubbed into “Related” for final reporting purpose.

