1.4. Benefit-Risk Assessment

Benefits

The clinical effect of efgartigimod was explored using clinical activity tools commonly used in MG clinical research and practice: total MG-ADL, QMG, MGC, and MG-QoL15r scores. A mean total score change from baseline in total MG-ADL, QMG, MGC, and MG-QoL15r scores was observed as early as day 8 in patients treated with efgartigimod. A long-lasting reduction in total MG-ADL and MGC scores was observed, with the reduction in total scores still seen at day 78 (end of study [EoS]). Efgartigimod showed a statistically significant reduction in total MG-ADL, QMG, and MG-QoL15r scores compared with placebo at specific time points, indicating a clinical improvement in efgartigimod treatment over placebo. For all MG scales, a greater maximum mean change from baseline (reduction) was observed in the efgartigimod treatment group compared with placebo.

Eligible participants of trial ARGX-113-1704 will be offered the option to roll over to this follow-on trial where (re-)treatment of efgartigimod can be done on an “as needed basis,” which is a substantial benefit for the patient.

Patients who have completed at least 1 cycle of treatment and at least 1 year of trial ARGX-113-1705 and have started Part B are eligible to enroll in the open-label trial ARGX-113-2002 to receive efgartigimod by SC administration. SC administration is considered more convenient for patients than IV administration, especially if efgartigimod can be administered by the patient or caregiver at home.

Risks

No major safety findings have arisen in the ongoing and completed trials, nor any pattern of AEs which would raise concerns or alter the potential benefit-risk profile of efgartigimod.

In the phase 3 trials in patients with gMG, the majority of TEAEs were reported as mild (grade 1) or moderate (grade 2) in severity. The most frequently ($\geq 5\%$) reported TEAEs during all cycles of efgartigimod 10 mg/kg treatment in the overall population who received at least 1 dose of efgartigimod were headache, nasopharyngitis, upper respiratory tract infection, diarrhea, urinary tract infection, nausea, myalgia, and oropharyngeal pain. TEAEs of severity of grade ≥ 3 that occurred in >2 patients who received efgartigimod were headache and myasthenia gravis. The only TEAE that led to efgartigimod discontinuation reported in >2 patients was myasthenia gravis. No SAEs were assessed by the investigator as related to efgartigimod treatment.

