Patients who have completed at least 1 cycle of treatment and at least 1 year of trial ARGX-113-1705 and have started Part B are eligible to enroll in the open-label trial ARGX-113-2002 to receive efgartigimod by SC administration.

Before enrolling in ARGX-113-2002 from Part B, patients must first complete the early discontinuation (ED) visit assessments specified in [Table 2](#). The previous efgartigimod IV dose must have been received at least 30 days before entry into ARGX-113-2002.

Patients can enroll in ARGX-113-2002 until recruitment for this study is closed. Patients who enroll in ARGX-113-2002 will not return to ARGX-113-1705.

(RE-)TREATMENT (Part A)

Each patient will start a (new) treatment period with efgartigimod when all of the following criteria are met:

- The patient has completed the previous treatment period (ie, after visit 4)
- The patient has a total MG-ADL score of ≥ 5 points with more than 50% of the total score due to non-ocular symptoms
- The patient has a reduction in the total MG-ADL score of < 2 points compared to the score at:
 1. The last treatment cycle baseline (TCB) in trial ARGX-113-1704 for the first treatment period (TP₁) in trial ARGX-113-1705
 2. The last treatment period Baseline (TP_nB) for all subsequent treatment periods (TP_{n+1}) in trial ARGX-113-1705

However, patients may not receive (re-)treatment with efgartigimod if, at the time of (re-)treatment, they have clinical evidence of bacterial, viral or fungal disease, or any other significant disease which could confound the results of the trial or put patients at undue risk. Patients who require an additional treatment but who are not eligible to receive (re-)treatment for the reasons listed here will remain in the trial to receive appropriate alternative MG treatment (see [Appendix 5](#) and [Appendix 6](#)).

Patients who have a treatment failure to efgartigimod for 3 consecutive treatment periods will be discontinued from the trial. Treatment failure means the absence of a decrease of at least 2 points in total MG-ADL score compared to the corresponding TP_nB in at least 50% of the assessments (ie, TP_nV2, TP_nV3, TP_nV4, and the first posttreatment period visit).

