5. TRIAL PROCEDURES

Every effort should be made to ensure that the protocol-required tests and procedures are completed as described. When a protocol-required procedure cannot be performed, the investigator will document the reason and any corrective and preventive actions that he/she has taken to ensure that the normal processes are adhered to in source documents. The trial team should be informed of these incidents in a timely manner.

Patients should be seen for all visits on the designated days or as closely as possible to the original planned visit schedule. There is a permissible window of ± 1 day for treatment period visits (visit 1 to visit 4), of ± 2 days for ITP_nV_n (Part A), and of ± 7 days for the ITPE_nV_n (Part B), EoA visit (day 365) and the EoS visit (day 1095 or when efgartigimod becomes commercially available or another option to access efgartigimod is available, whichever option comes first). Every effort should be made to schedule every visit on the exact day (which is relative to the baseline visit [SEB, TP_nB or TPE_nB]) within the window as described in the General Schedule of Assessments for Part A (Table 1) and for Part B (Table 2).

Each treatment period consists of 4 weekly infusions over a period of 3 weeks.

The SEB will be set at the first trial visit, while the baseline of each subsequent treatment period (TP_nB or TPE_nB) will be set at visit 1 of each corresponding treatment period.

At all visits, assessments of disease severity should be performed first, before any other trial-specific assessments, with the only exception of obtaining informed consent at SEB and the weight assessment. The MG-ADL scale needs to be performed prior to the QMG scale (Part A) as per Table 1. Acetylcholinesterase inhibitors must be halted for at least 12 hours before the QMG assessment (Part A).

As from signature of informed consent until last study visit, all AEs that occur and all concomitant medications, whether allowed or not, that are taken during the trial are to be recorded on the appropriate pages in the electronic case report form (eCRF).

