5.1. Informed Consent and Roll-Over Visit

The roll-over visit (SEB) can be either ITP₀V₁ or TP₁V₁, depending on the patient status regarding the need for (re-)treatment upon roll-over from trial ARGX-113-1704. The first visit in trial ARGX-113-1705 will always coincide with the last visit in trial ARGX-113-1704.

The patient must sign the informed consent form (ICF) prior to any trial-related assessment. The assessments done for the last visit in trial ARGX-113-1704 should not be repeated.

Prior to signing the ICF, trial patients will be instructed not to participate in any other clinical trial that involves an intervention or collection of data until the completion of the current trial.

After informed consent has been obtained, participants of trial ARGX-113-1704 will be screened at the site for eligibility to roll over to this trial based on the inclusion and exclusion criteria defined in Sections 4.3.1 and 4.3.2, respectively.

In addition to obtaining written informed consent and the eligibility check, the following assessments will be performed at SEB:

- Clinically relevant medical and surgical history, clinically relevant prior treatments and all concomitant medications (see Sections 6.8 and 7.2.5)
- Demographic characteristics (date of birth, sex, race, and ethnicity, per national regulations)
- Assessments of disease severity – the MG-ADL scale should be administered before the QMG scale
- Suicidal ideation and behavior will be assessed via a targeted question based on the Patient Health Questionnaire item 9 (PHQ-9)¹⁷
- Complete physical examination, including at a minimum: general appearance, skin, lymph nodes, musculoskeletal/extremities, abdomen, cardiovascular, respiratory, and neurological systems
- Weight and height
- Vital signs (supine blood pressure, heart rate, body temperature). It is recommended that the method used to measure body temperature at SEB is maintained throughout the trial for each patient
- ECG (heart rate, PR, QT, and QRS interval)
- Clinical laboratory tests (see Appendix 3 for an overview of the clinical laboratory tests that will be assessed). Patients need to have fasted at least 8 hours prior to sampling
- Urinalysis
- Urine pregnancy test (only for women of childbearing potential, see DEFINITION OF TERMS)

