
SYNOPSIS Criteria for Evaluation:
 
3. TRIAL ENDPOINTS
 
3.1. Primary Endpoint
 
3.2. Secondary Endpoint
 
3.3. Tertiary Endpoints
	
Primary Endpoint:
 
 Incidence and severity of AEs, SAEs, vital signs, electrocardiogram (ECG) and laboratory assessments over 1 year in AChR-Ab seropositive patients. 
Secondary Endpoints:
 
 Incidence and severity of AEs, SAEs, vital signs, ECG and laboratory assessments over 1 year in the overall population (AChR-Ab seropositive patients and AChR-Ab seronegative patients). Incidence and severity of AEs, SAEs, vital signs, ECG and laboratory assessments at each Treatment Period in AChR-Ab seropositive patients. Incidence and severity of AEs, SAEs, vital signs, ECG and laboratory assessments at each Treatment Period in the overall population (AChR-Ab seropositive patients and AChR-Ab seronegative patients). 
Tertiary Endpoints
 
 To evaluate the disease severity as assessed by total MG-ADL score changes compared to SEB and the corresponding TP_nB in AChR-Ab seropositive patients. To evaluate the disease severity as assessed by total MG-ADL score changes compared to SEB and the corresponding TP_nB in the overall population (AChR-Ab seropositive and AChR-Ab seronegative patients). To evaluate the disease severity as assessed by total QMG score changes compared to SEB and the corresponding TP_nB in AChR-Ab seropositive patients. To evaluate the disease severity as assessed by total QMG score changes compared to SEB and the 	
Endpoints streamlined to reflect what will actually be summarized and labels added to clarify what will be analyzed in Part A and Part B of the trial.
 
Corrected to reflect that changes from the treatment period baseline of the first cycle will be summarized (instead of changes from SEB) as patients might start the study with an intertreatment period.
 
“To evaluate the disease severity as assessed by” should not be part of an endpoint definition.
 
For Part B only immunogenicity will be characterized as a tertiary endpoint. Furthermore, only safety and tolerability will be followed up and no PD markers will be summarized.

Section	Change	Rationale

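### Whether non-serious MG worsening can be reported as an AE depends on the patient's MG-ADL score at study entry, which risks differential under-reporting in the primary endpoint

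*Protocol*

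**What the plan says.** The primary endpoint is the incidence and severity of AEs, SAEs and other safety measures in AChR-Ab seropositive patients (Protocol Section 3.1). The secondary endpoint is the same in all patients (Section 3.2).

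Section 7.2.1 contains two rules that bear on MG worsening:

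- **General rule.** An AE can be an "exacerbation of an existing disease (a worsening in the character, frequency, or severity of a known condition), if considered clinically relevant by the investigator". There is no score test.
- **MG-specific rule.** Clinically relevant MG worsening can be reported as an AE "provided that it is supported by a clinically relevant change in total MG-ADL score (as compared to SEB". The size of a clinically relevant change is not given.

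On the reference score, Section 5 states: "The SEB will be set at the first trial visit". Section 5.1 places that visit at ITP0V1 or TP1V1, "depending on the patient status regarding the need for (re-)treatment upon roll-over from trial ARGX-113-1704". The trial can last 3 years, and SEB stays the same throughout.

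To start treatment in Part A, Section 4.1 requires, among other things: "The patient has a total MG-ADL score of ≥ 5 points with more than 50% of the total score due to non-ocular symptoms". The total must also be less than 2 points below the last cycle baseline of the parent trial (for TP1) or the last treatment period baseline (for later periods).

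SAP Section 5.1.3 tabulates AEs by AChR-Ab status and cycle and only lists those in ITP0. No table splits them by entry status.

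**The concern.** Patients here are treated, improve, and are treated again when their scores rise. SEB is one point in that course, and it is not the same point for everyone. A patient who enters needing treatment tends to have a high reference score, and one who enters without starting treatment can have a low one. A test of change from SEB therefore asks more of the high-SEB patient before the same deterioration may be called an AE.

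MG events are prominent in the safety profile. Section 1.4 names MG as one of two grade 3 or higher events seen in more than 2 patients, and adds: "The only TEAE that led to efgartigimod discontinuation reported in >2 patients was myasthenia gravis". If recording depends on the entry score, the MG count partly reflects when in the disease course each patient rolled over.

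The amendment log shows that the sponsor met this difficulty with the score endpoints. These now use the first treatment period baseline, "instead of changes from SEB) as patients might start the study with an intertreatment period". The AE rule in the current text still uses SEB.

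**Working it through.** The plan gives no expected MG event rate, power or sample size calculation, so there is no figure to reproduce. The check applies the rules to example scores.

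**Inputs**
- MG-ADL total: 0 to 24, higher is worse (Protocol Section 7.1.1).
- Score condition: event score − SEB ≥ d. Because d is not stated, I assume d = 2, taken from the phase 2 definition of a clinically relevant reduction (Section 1.2), with a range of 1 to 3.
- Part A score criteria for re-treatment: total ≥ 5, and last baseline − score < 2 (Section 4.1).
- The patient scores are illustrative.

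**1. Score at which the condition is met (SEB + d)**

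| SEB | d = 1 | d = 2 | d = 3 |
|---|---|---|---|
| 3 | 4 | 5 | 6 |
| 5 | 6 | 7 | 8 |
| 8 | 9 | 10 | 11 |
| 10 | 11 | 12 | 13 |
| 12 | 13 | 14 | 15 |
| 23 | 24 | not possible | not possible |
| 24 | not possible | not possible | not possible |

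**2. The same flare, two entry scores**
- Both patients stand at 3 and rise to 10, a worsening of 10 − 3 = 7.
- SEB 10: 10 − 10 = 0, which fails at d = 1, 2 and 3. With d = 2 the score must reach 12, a rise of 12 − 3 = 9.
- SEB 3: 10 − 3 = +7, which passes at d = 1, 2 and 3. With d = 2 the condition is met at 5, a rise of 2.

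**3. Overlap with re-treatment.** If the last baseline equals SEB = S, re-treatment is open from max(5, S − 1), while the AE condition needs S + 2. Scores that meet the re-treatment score criteria but fail the AE condition are 5–6 for S = 5, 7–9 for S = 8, 9–11 for S = 10 and 11–13 for S = 12.

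**4. Is the split one of relapse versus remission?** No. With a parent-trial baseline of 12, a score of 10 is a reduction of 2 and does not qualify for treatment, so that patient enters at ITP0V1 with SEB 10. What matters is the SEB value. Entry status is only a proxy for it.

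**5. Set against the rescue criteria.** Section 6.8.2 accepts new or worsening respiratory or bulbar symptoms, or a 2-point rise in individual non-ocular items, together with the physician's view that health is in jeopardy. Neither route refers to the total score or to SEB. Take SEB 10 and a current total of 3. If swallowing goes from 0 to 2 and nothing else changes, the total is 5, and 5 − 10 = −5. Such a patient could be rescued and discontinued (Sections 4.4 and 6.8.2) while the worsening fails the AE condition.

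**6. Which reference removes the difference?**
- Last score before the event (3 in step 2): +7 for both patients.
- Treatment period baseline: no help, because it is itself a treatment-need score. A baseline of 10 again gives 0.
- Lowest score in the cycle: +7 for both. But a patient who falls at least 3 points and then meets the re-treatment rule (score ≥ baseline − 1) has risen at least (baseline − 1) − (baseline − 3) = 2. With d = 2, every such planned re-treatment would pass the score test.

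**The case against.** **Under-counting is not shown.** This stands. A reader might infer that the primary endpoint does under-count MG exacerbations. The documents do not say how many patients enter each way or how often they flare, and Section 1.4 shows that MG events do reach the AE data.

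**Serious events are not lost.** This also stands. Section 7.2.1.2 requires any SAE to be reported within 24 hours, without a score test. What remains is that the SAE definition excludes hospitalisation for an illness present before enrolment unless it deteriorated unexpectedly. How that applies to MG should be spelled out.

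**A return to the entry score is the planned course.** In Part A it is the re-treatment trigger, and nothing says each such return is an AE. Asking for worsening beyond entry status is a defensible way to separate events from expected cycling. It would serve that purpose evenly only if SEB meant the same thing in every patient. For the same reason, a reader might infer that expected relapses inflate the count in ITP0V1 entrants. The documents do not support that either: they do not say whether such returns count, and AEs before the first dose are only listed.

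**The general definition already admits these flares.** If it governs, nothing is lost; if the MG sentence governs, it narrows the general rule. The text does not say which, and a site can reasonably apply the MG-specific sentence to MG.

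**The amendment log does not endorse another AE reference.** Correct. For TP1V1 entrants the first treatment period baseline coincides with SEB. The log shows only that the sponsor recognised that SEB can fall in an intertreatment period.

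**The scores remain available.** In part. The SAP summarises and lists MG-ADL totals, and rescued patients appear in disposition. But SAP Section 4.1.2 pools all worsening into one category above 0, so these tables do not replace a count of worsening events.

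**Conclusion.** The point holds as a risk to ascertainment. Under the current text, whether a non-serious MG worsening may be recorded as an AE depends on the patient's entry score. The MG-specific condition conflicts with the general AE definition, and a worsening that leads to rescue and discontinuation in Part A could fail it. The consequence is possible differential under-reporting of non-serious MG worsening in the primary and secondary AE endpoints.

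The number of events affected cannot be computed from the documents. The illustration rests on an assumed 2-point threshold and on chosen scores; its contrast (0 against +7) is the same for thresholds of 1 to 3. It does not follow that the endpoint is known to be biased, that serious MG events go unreported, or that the two entry groups are a relapse group and a remission group.

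**What to change.** 1. In Section 7.2.1, replace the comparison with SEB by a comparison with the last assessment before the event. Keep the investigator's assessment of clinical relevance, state the size of change meant, and say whether an expected end-of-cycle return that only triggers planned re-treatment counts as an AE.
2. State that MG worsening that is serious, or that leads to rescue or discontinuation, is recorded as an AE whatever the MG-ADL change. Reconcile this with the general AE definition, the hospitalisation exclusion in the SAE definition, and the reporting rule in Section 7.2.1.2.
3. For data already collected, tabulate TEAEs with preferred term myasthenia gravis (patients, events, rate per patient-year) by entry at TP1V1 versus ITP0V1.

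The cost is a few sentences in the protocol and the AE completion guidance, one extra table, and somewhat more MG-worsening AEs on record. Two limits should be noted. A last-assessment reference can miss a slow rise of 1 point per visit, which is one reason to state which AE rule governs. The table cannot recover unrecorded events, and because the entry groups may also differ in disease state, a difference between them would be a signal rather than proof of reporting bias.
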